5.4. Multiple Comparisons and Multiplicity

No adjustments for multiplicity will be made.

5.5. Display order of Echocardiography endpoints (source: SI.CV)

Whenever multiple Echocardiography endpoints (found in the CV dataset) are required within the same Table/Listing/Figure and the display ordering is not explicitly stated the following display ordering should be apply:

Priority Order of presentation	CVTSTCD	Description (Note: the actual label/text would be taken from dataset manager at the time of reporting)
1 (1 st in T/L/F)	AH001CAL	Pulmonary Artery Systolic Pressure
NA	AH001	Pulmonary Artery Systolic Pressure (eCRF)
2	AK001	Ratio of RV to LV End-Diastolic Area
3	AK002	Paradoxical Septal Motion
4	AK015	Have PCD or ACP
5	AK016	Severity of PCD or ACP
6	AK003	Systolic Eccentricity Index
7	AK006	Max Velocity S Wave at Tricuspid Annulus
8	AK007	Fractional Area Contraction
9	AK008	Acc Time of RV Ejection Flow (Tacc)
10	TAPSE	Tricuspid Annular Plane Systol Excursion
11	AK004	Transtricuspid Pressure Gradient (TPG)
12	AK009	Mean Acc of RV Ejection Flow at End Exp
13	AK010	Mean Acc of RV Ejec Flow at End Exp-Insp
14	AK005	IVC Diameter at End Expiration
15	AK011	Respiratory Variations of RV VTI
16	AK012	Respiratory Variations of SVC Diameter
17	CARDOUT	Cardiac Output (CO)
18	LVEJ	Left Ventricular Ejection Fraction
19	AK013	LV Velocity (E') Tissue of Annulus
20	AK014	LV Early to Late Filling Velocities
21	ERATRIAP	Estimated Right Atrial Pressure
22	AI001	Measured Right Atrial Pressure
23	RAP	Right Atrial Pressure
24	AD003	Central Venous Pressure (CVP)
NA	AH001src	<Do not display; variable used to track source of PASP>

Note: Only display AH001CAL but label it using the AH001 label text (this is because the auto derived eCRF value for PASP; supplied as AH001; may not capture all data cases reliably and so will be re-calculated)

5.6. Other Considerations for Data Analyses and Data Handling Conventions

Other considerations for data analyses and data handling conventions are outlined in the appendices:

Section	Component
10.3	Appendix 3: Assessment Windows
10.4	Appendix 4: Study Phases and Treatment Emergent Adverse Events
10.5	Appendix 5: Data Display Standards & Handling Conventions
10.5	Appendix 6: Derived and Transformed Data
10.7	Appendix 7: Reporting Standards for Missing Data
10.8	Appendix 8: Values of Potential Clinical Importance

6. STUDY POPULATION ANALYSES

6.1. Overview of Planned Study Population Analyses

The study population analyses will be based on the Enrolled population, unless otherwise specified.

Study population analyses including analyses of participant disposition, protocol deviations, demographic and baseline characteristics, and prior and concomitant medications will be based on GSK Core Data Standards. Details of the planned displays are presented in [Appendix 10: List of Data Displays](#).

Note: Local French law prohibits the collection of Race information, so the race/ethnicity variables would be blank in the datasets and displays.

7. PHARMACODYNAMIC AND BIOMARKER ANALYSES

7.1. Primary Pharmacodynamic/Biomarker Analyses

7.1.1. Endpoint / Variables

The following variables may be included in the statistical model:

- Independent variable of interest:
 - Ang II on Study Days 1, 2 and 3 (after any imputations)
- Dependent (bivariate) variable of interest:
 - PASP on Study Days 1, 2 and 3
 - RV size ratio on Study Days 1, 2 and 3
- Potential covariates (to be explored, order listed indicates expected importance):
 - Centre
 - Age at screening
 - Sex
 - Use of vasopressors on Study Days 1, 2 and 3
 - PEEP on Study Days 1, 2 and 3
 - Proning status on Study Days 1, 2 and 3
 - BMI at screening
 - Concurrent use of inhaled nitric oxide on Study Days 1, 2 and 3
 - Mean airway pressure on Study Days 1, 2 and 3
 - Tidal Volume on Study Days 1, 2 and 3
 - ECMO on Study Days 1, 2 and 3
 - ECCO2R on Study Days 1, 2 and 3
 - SAPS II at screening
 - PaO₂/FiO₂ on Study Days 1, 2 and 3

Additionally, the presence/absence of paradoxical septal motion on Study Days 1, 2 and 3 may be assessed on an informal visual basis.

Note: Since the study was terminated early there may not be sufficient information in the collected data to explore covariate analyses and the covariate exploration process may not take place at all.

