4. OBJECTIVES AND ENDPOINTS

Objectives	Endpoints
Primary	

 To evaluate the association between plasma Ang II levels and RV function in mechanically ventilated participants. 	
 Ang II levels Echocardiographic measures: 
 Ratio of right ventricular to left ventricular end-diastolic area Paradoxical septal motion PASP estimated from transtricuspid pressure and right atrial pressure or IVC diameter (whichever is available) 
Up to and including Day 3 of observation

Secondary	

 To define the incidence of ACP and PCD in mechanically ventilated participants. 	
 Presence of PCD, ACP (severe PCD) and severe ACP 
Up to and including Day 3 of observation

 To evaluate the association between plasma Ang(1-7) levels, AngII/Ang(1-7) ratio and RV function in mechanically ventilated participants. 	
 Ang(1-7) levels Ang II/Ang(1-7) ratio Echocardiographic measures: 
 Ratio of right ventricular to left ventricular end-diastolic area Paradoxical septal motion PASP estimated from transtricuspid pressure and right atrial pressure or IVC diameter (whichever is available) 
Up to and including Day 3 of observation

Objectives	Endpoints
Exploratory	

 To evaluate the association between plasma Ang II and Ang(1-7) levels and other measures of right ventricular function in mechanically ventilated participants. 	
 Ang II, Ang(1-7) levels Echocardiographic measures: 
 Paradoxical septal motion (systolic eccentricity index) Maximal velocity of s wave (tissue Doppler imaging) at the tricuspid annulus Fractional area contraction (end diastolic area minus end systolic area normalised to end diastolic area) Acceleration time of RV ejection flow Mean acceleration of RV ejection flow (maximum velocity/acceleration time) at end-expiration and end-inspiration Inferior vena cava diameter at end-expiration Respiratory variations of RV velocity time integral (end-expiration minus end-inspiration normalised to end-expiration) Tricuspid annular plane systolic excursion (TAPSE)

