10.3. Statistical Analyses

10.3.1. Pharmacodynamic Analyses

Endpoint	Statistical Analysis Methods
Primary	
The association of Ang II with RV function (measured by PASP and RV size ratio) will be modelled using a Bayesian repeated measures mixed effects linear regression model, where PASP and RV size ratio are joint response variables, and including subject as a random effect and log(Ang II), age and sex as fixed effects. The model will be used to make a probabilistic prediction of PASP and RV size ratio for two reference values of Ang II, and hence an estimate for the probability of RV dysfunction (defined as PASP > 40 mmHg or RV size ratio > 0.6, following Boissier 2013) for the two given Ang II levels will be obtained using mean values for the other continuous covariates and averaging over all levels of class effects for categorical covariates.
 
The above modelling may use a modified Ang II value (modification based on the corresponding Ang(1-7) result to account for potential inhibitory interactions); details to be provided in the reporting and analysis plan (RAP).
 
The primary analysis will use the Evaluable population.

Secondary	
Association of Ang(1-7) with RV function (measured by PASP and RV size ratio) and of Ang II/Ang(1-7) with RV function (measured by PASP and RV size ratio) will both be modelled as per the primary analysis described above. These analyses will be done using the Evaluable population.
 
A model including both Ang II and Ang(1-7) as co-predictors of RV function may also be built, to explore the relationship between RV function and the envisaged dual action of angiotensin converting enzyme (ACE)2 effecting a reduction in Ang II together with a simultaneous increase in Ang(1-7).
 
Incidence of PCD and ACP during the three days of the study period and prevalence of pre-existing PCD/ ACP on entry to the study will be reported with 95% confidence intervals. This analysis will be done using the Completed population (which includes a clause to include participants who have an onset of PCD/ ACP but are subsequently withdrawn from the study before all three days' worth of data are collected without withdrawing consent).
 
The distribution of PASP, RV size ratio and other measurements of RV function in mechanically ventilated participants will be assessed via a combination of descriptive summary tables and outputs from the statistical modelling.

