2.2. Study Objective(s) and Endpoint(s)

[figure not shown]
Exploratory objectives/endpoints have been included for completeness, but due to the early termination of the study will not be analysed further (unless they naturally form part of an output related to a primary or secondary objective, in which case they may be included on a case by case basis).

Objectives	Endpoints
Primary Objectives	Primary Endpoints

 To evaluate the association between plasma Ang II levels and RV function in mechanically ventilated participants. 	
 Ang II levels Echocardiographic measures: 
 Ratio of right ventricular to left ventricular end-diastolic area

Objectives	Endpoints
	
 Paradoxical septal motion Pulmonary arterial systolic pressure (PASP) estimated from transtricuspid pressure and right atrial pressure or inferior vena cava (IVC) diameter (whichever is available) 
Up to and including Day 3 of observation

Secondary Objectives	Secondary Endpoints

 To define the incidence of ACP and PCD in mechanically ventilated participants. To evaluate the association between plasma Ang(1-7) levels, Ang II/ Ang(1-7) ratio and RV function in mechanically ventilated participants. 	
 Presence of PCD, ACP (severe PCD) and severe ACP 
Up to and including Day 3 of observation
 
 Ang(1-7) levels Ang II/ Ang(1-7) ratio Echocardiographic measures: 
 Ratio of right ventricular to left ventricular end-diastolic area Paradoxical septal motion PASP estimated from transtricuspid pressure and right atrial pressure or IVC diameter (whichever is available) 
Up to and including Day 3 of observation

Exploratory Objectives	Exploratory Endpoints

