7.1.2. Summary Measure

The posterior predictive probability of RV dysfunction in a hypothetical individual for a pre-determined “pre-dose” Ang II value,

The posterior predictive probability of RV dysfunction in a hypothetical individual for a pre-determined “post-dose” Ang II value, and

The difference between the above two probabilities.

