7.1.5. Statistical Analyses / Methods

The purpose of the primary analysis is to evaluate the association of biomarkers of the Renin Angiotensin System (RAS), specifically Ang II but secondarily Ang(1-7) with measures of RV function (specifically PASP and RV size ratio in the primary model, and also paradoxical septal motion on a more informal visual basis), whilst taking into account any observable variables that may confound the relationship between the two concepts.

RV function will be measured using PASP and RV size ratio. The general principle underlying all the analyses of RV function and RAS peptide biomarkers will be:

- model the joint distribution of PASP and RV size ratio as a function of the RAS peptide(s) in question (together with confounding variables also included as covariates),
- choose reference values of the RAS peptide(s) in question and estimate a posterior distribution of PASP and RV size ratio for those given values, and
- use the posterior distribution to determine the probability of RV dysfunction (for a future individual participant), defined (following the definition of moderate/severe pulmonary circulatory disease given in [Boissier, 2013](#)) as:
 - PASP > 40 mmHg
 - RV size ratio > 0.6

The advantage of this method is that all the information on the continuous scales of PASP and RV size ratio is maintained throughout the modelling process, and that dichotomising

participants into binary categories takes place at the end after the modelling has been done.

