7.1.5.1. Statistical Methodology Specification

Endpoint / Variables

 See above
Model Specification

 See above
Model Checking & Diagnostics

 “Bayesian Statistics Best Practice at GSK – Clinical Trials using Bayesian Inference” (effective 20-Apr-2017) gives guidance on model checking and diagnostics that would be applicable to the MCMC modelling in this study.
Model Results Presentation

 See above
Subgroup Analyses

 Not planned.
Sensitivity and Supportive Analyses

 See above. Only the final (chosen) model form would be used to produce the Tables/Listings/Figure outputs supporting the CPSR. If the joint modelling strategy fails then an alternative strategy would be to derive the RV

dysfunction status for each participant (using the same criteria) and analyse the collection of derived binary outcomes, accounting for the repeated measures made on each participant (e.g. logistic regression modelling techniques). The final logit model (including any covariates) would be used to determine the probabilities (and differences) for the sets of “pre and post” dose Ang II reference values to be fed into the decision-making criteria. Any such approach would be documented in the CSR.

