10.10.7. Pharmacodynamic and Biomarker Figures

Pharmacodynamic and Biomarker: Figures					
No.	Population	IDSL / Example Shell	Title	Programming Notes	Deliverable [Priority]
Echocardiography					
3.1.	Evaluable	PD_F2 (SCAT3D_YN)	Scatterplot of PASP vs RV Size Ratio marked by Paradoxical Septal Motion Status	Scatterplot of (x-axis) PASP vs (y-axis) RV size ratio. Paradoxical Septal Motion Status is marked by black(Y)-grey(N) colour. For Not Done PSM status leave blank (i.e. do not plot a coloured circle within the data point)	SAC 1
RAS Biomarkers					
3.2.	Evaluable	PD_F1 (SCAT2D)	Scatterplots of Ang II, Ang(1-7) and Ang(1-5) combinations	Display with a Log10-transformed x and y axis scales. Separate page/plot for each combination. Present Ang II Vs Ang(1-7), Ang II Vs Ang(1-5) and Ang(1-7) Vs Ang(1-5) in listed order	SAC 1
3.3.	Evaluable	PD_F4 (SERIES1D)	Individual Line Plots of RAS Biomarkers by Timepoint	On separate pages, time series plots for RAS biomarker readouts: Ang II, Ang(1-7), Ang(1-5), Ang II/Ang(1-7) ratio per visit (use log10 scale for y-axis). If the number of subject is too large omit the legend.	SAC 1

Pharmacodynamic and Biomarker: Figures					
No.	Population	IDSL / Example Shell	Title	Programming Notes	Deliverable [Priority]
3.4.	Evaluable	PD_F2 (SCAT3D_YN)	Scatterplots of Selected Echocardiography Endpoints Vs selected RAS biomarkers by Paradoxical Septal Motion Status	On separate pages, scatterplots of (x-axis) RAS biomarker readouts: Ang II, Ang(1-7), Ang(1-5), Ang II/ Ang(1-7) ratio (using log10 axis scale), vs (y-axis) PASP and RV size ratio readouts. Paradoxical Septal Motion Status is marked by black(Y)-grey(N) colour. For Not Done PSM status leave blank (i.e. do not plot a coloured circle within the data point)	SAC 1
3.5.	Evaluable	PD_F3 (SCAT3D_CONT)	Scatterplots of PASP vs. RV Size Ratio marked by RAS biomarker levels	On separate pages, scatterplots for (x-axis) PASP vs (Y-axis) RV size ratio coloured by RAS biomarker readouts: Ang II, Ang(1-7), ANG II/ Ang(1-7) ratio and Ang(1-5) on rainbow colour scale (no log-transformation). For each RAS biomarker scatterplot without and with visit marks provided.	SAC 1

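### Paradoxical septal motion is listed as a primary echo measure, but no named output estimates its association with Ang II with an interval

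*SAP*

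**What the plan says.** The primary objective is "To evaluate the association between plasma Ang II levels and RV function in mechanically ventilated participants" (protocol section 4). Under it, both protocol section 4 and SAP 2.2 list "Paradoxical septal motion" beside the RV/LV area ratio and PASP. Protocol 3.2 likewise names septal kinetics, with RV size and pulmonary hypertension, among the echo features by which the hypothesis will be tested.

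The analysis sections are narrower:

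- Protocol 10.3.1 specifies a Bayesian repeated-measures model "where PASP and RV size ratio are joint response variables".
- SAP 7.1.5 keeps those two responses, "and also paradoxical septal motion on a more informal visual basis". SAP 7.1.1 makes even the visual assessment optional: "the presence/absence of paradoxical septal motion on Study Days 1, 2 and 3 may be assessed on an informal visual basis".
- The summary measure in SAP 7.1.2 is "The posterior predictive probability of RV dysfunction in a hypothetical individual for a pre-determined" pre-dose or post-dose Ang II value, and the difference between the two. RV dysfunction is defined from PASP and RV size ratio only.
- If joint modelling fails, SAP 7.1.5.1 would derive RV dysfunction by the same criteria and "analyse the collection of derived binary outcomes, accounting for the repeated measures made on each participant". Septal motion is absent there too.

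Septal motion does appear in other outputs. Table 3.1 summarises qualitative echo measures by timepoint. Listing 13 covers it, since it is not among the stated exclusions. In Figures 3.1 and 3.4, "Paradoxical Septal Motion Status is marked by black(Y)-grey(N) colour".

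**The concern.** A measure named under the primary objective should have a stated way of answering that objective. Here the question is association with Ang II, and for septal motion the only route is to look at coloured points. A plot gives neither the size of an association nor its uncertainty, and with few positive participants two readers can reasonably disagree about what it shows.

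The feature also carries clinical information that the modelled composite does not. Protocol 9.5.3 uses septal dyskinesia to separate ACP from moderate PCD, whereas the composite (PASP above 40 mmHg or RV size ratio above 0.6) makes no such distinction.

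What is at stake is completeness of reporting on one listed measure. No decision rule depends on it.

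**Working it through.** **1. Does septal motion enter the primary quantity?** Protocol Table 1b can be reproduced without it. Inputs (protocol 12.5.3 and 12.5.4): mean log Ang II 2.78, SD 1.74; PASP mean 38, SD 8; RV size ratio mean 0.61, SD 0.15; outcome correlation 0.5; reference values 55.4 and 7.1 pg/ml.

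For each reference value, z = (ln(Ang II) − 2.78)/1.74, which gives 0.71 at 55.4 and −0.47 at 7.1. Given z, the two outcomes are bivariate normal, with means 38 + 8·r1·z and 0.61 + 0.15·r2·z, variances 64(1 − r1²) and 0.0225(1 − r2²), and covariance (0.5 − r1·r2)·8·0.15. Here r1 and r2 are the correlations of log Ang II with PASP and with RV size ratio. Then P(RV dysfunction) = 1 − P(PASP ≤ 40 and ratio ≤ 0.6).

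| r1, r2 | Computed difference, points | Table 1b |
|---|---|---|
| 0, 0 | 0.0 | 0.3 |
| 0.6, 0.6 | 34.1 | 33.9 |
| 0.3, 0.3 | 14.9 | 14.9 |
| 0.3, 0 | 6.0 | 6.1 |
| 0.6, 0 | 13.4 | 13.2 |
| 0.6, 0.3 | 22.8 | 22.5 |
| 0, 0.3 | 9.4 | 9.1 |
| 0, 0.6 | 22.6 | 22.5 |
| 0.3, 0.6 | 26.7 | 26.9 |

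All nine agree to within 0.3 points. PASP and RV size ratio account for the whole decision quantity.

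**2. Does any other named output estimate the association?**

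- Table 3.1: summarises by timepoint, not against Ang II.
- Listing 13: individual values only.
- Figures 3.1 and 3.4: colour only. Figure 3.4 has Ang II on an axis, but no estimate is specified.
- Table 5.1: correlations of RAS biomarkers with pharmacodynamic endpoints (mixed-model, Pearson, Spearman). Septal motion is not named and no method for a yes/no variable is given.
- Table 5.3: RAS biomarkers by categorical covariates, to be chosen at analysis. Septal motion is not named.
- Systolic eccentricity index, the continuous septal measure: exploratory, and SAP 7.3 plans no exploratory analyses.

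**3. How precise could an estimate be?** The documents give neither septal-motion prevalence p nor the final N. Assume p from 5% to 25%, N = 50 for illustration, and one record per participant. For modest effects, the SE of the log odds ratio per SD of log Ang II is about 1/√(N·p·(1 − p)), and the 95% interval is the estimate multiplied or divided by exp(1.96·SE).

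| p | Expected cases | SE | Factor |
|---|---|---|---|
| 5% | 2.5 | 1/√2.375 = 0.649 | 3.6 |
| 10% | 5 | 1/√4.5 = 0.471 | 2.5 |
| 25% | 12.5 | 1/√9.375 = 0.327 | 1.9 |

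At N = 25 the factors for 5% and 25% are 6.0 and 2.5; at N = 150 they are 2.1 and 1.45.

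For a ratio of geometric means, the SE on the natural-log scale is SD·√(1/(Np) + 1/(N(1 − p))) = SD/√(Np(1 − p)). With the protocol's SD of 1.74 and N = 50, the factors are exp(1.96·1.74·0.649) = 9.1, exp(1.96·1.74·0.471) = 5.0 and exp(1.96·1.74·0.327) = 3.0. With only two or three cases, these approximations are optimistic.

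**The case against.** The best defence is that this is a deliberate and open choice. Protocol 10.3.1 and 10.3.3 define the primary analysis of RV function by PASP and RV size ratio, Appendix 5 simulates only those two, and the SAP says plainly that septal motion is handled informally. The study tests no formal hypotheses (SAP 2.4), its interim analyses are cancelled, and no criterion uses septal motion. All of that stands and limits the importance of the point. It does not reconcile the endpoint lists with the analysis. Early termination is not the cause either, since the omission is already in protocol 10.3.1, and the SAP introduction keeps primary and secondary endpoints in scope.

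Several stronger readings are tempting but not supported:

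- *The primary objective has no estimate, or the SAP dropped a primary endpoint.* The objective has a specified model and summary measure, and the SAP follows protocol 10.3.1.
- *Optional coloured plots are all that septal motion receives.* A descriptive table and a listing are also planned, and Figures 3.1 and 3.4 are first-priority deliverables not marked conditional. Only the wording of SAP 7.1.1 makes the assessment optional.
- *About 5 of 50 participants would show it, from the 10% ACP rate in protocol 10.1.* Under protocol 9.5.3, ACP needs a dilated RV as well as septal dyskinesia. If dyskinesia and paradoxical motion are taken as the same finding, the ACP rate is only a lower bound. The figure of 50 is the size of a cancelled interim.
- *The SAP's fallback logistic model can simply be reused.* It was meant for a common outcome: under Appendix 5, RV size ratio alone exceeds 0.6 with probability P(Z > (0.6 − 0.61)/0.15) = P(Z > −0.067), about 53%. With a handful of positive participants, a model with age, sex and repeated days may not be estimable. SAP 7.1.1 already warns that covariates may not be explored even in the primary model.

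**Conclusion.** The point holds in a limited form. Septal motion is listed under the primary objective in both documents, yet no named output gives its association with Ang II as an estimate with an interval. Descriptive reporting is planned, and the primary model is unaffected.

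The precision figures rest on an assumed prevalence of 5% to 25%, an illustrative 50 participants and one record each. They show that any estimate would be imprecise, perhaps very imprecise. That argues for a simple method and a supportive label. It does not favour a plot, which leaves the same imprecision unstated. The point is minor and worth acting on because the remedy is cheap.

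**What to change.** In SAP 7.1.1 and 7.1.5, replace the informal visual assessment with a specified estimate, and keep the figures as illustration:

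1. Report geometric mean Ang II by septal-motion status (Y/N), with a 95% interval that accounts for repeated days within participant. State the number of participants and of participant-days in each group.
2. If the number of positive participants allows, fit a repeated-measures logistic model of septal motion on log10 Ang II with a weakly informative prior. Add age and sex only if that model can be fitted. Report the odds ratio, and the predicted probabilities at the two Ang II reference values in SAP 7.1.5, with 95% credible intervals.
3. Label both as supportive.

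The selected septal-motion value for each day is already derived (SAP 10.6.6, Table 4), so no new data are needed. The cost is one extra table. The downside is a wide interval that, for the logistic model, may depend on the prior. If the sponsor prefers no added analysis, the minimum is a sentence in SAP 2.1 and 2.2 stating that septal motion is descriptive only. That would remove the inconsistency but leave the association unestimated.
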